Between 20% and 40% of patients report no clinically relevant improvement after spinal fusion (minority class).^{5,10,12,15} For sample size calculation, we take 20% for a conservative estimate. Consequently, for this study, based on our expertise and on the rules of thumb mentioned above, we estimate that a minimum of 200 patients with a negative outcome (minority class) are required to extract generalizable feature relationships. With an estimated incidence of approximately 20% as explained above, that means that a minimum of around **1000 patients are required for training. For adequate evaluation of calibration at external validation, we estimate that another 300 patients will be required** (thus, approximately 60 patients with a positive outcome). Thus, in total, we estimate that **a minimum of 1300 patients** are necessary to arrive at a robust model. More data will likely lead to greater performance and better calibration.

Predictive Modeling

A KNN imputer will be co-trained to impute any missing data that may occur in future application of the model. If there is missing data in the training set, it will be imputed using said KNN imputer.¹⁶ Features or patients with a missingness greater than 25% will be excluded. Data will be standardized and one-hot-encoded. In case of major class imbalance – which is expected for the abovementioned endpoint – random upsampling or synthetic minority oversampling (SMOTE) will be applied to the training set.^{17,18} All features will initially be provided to the model for training. If necessary, we will apply recursive feature elimination (RFE) to select input features on the training data.¹⁹

We will trial the following algorithms for binary classification: Generalized linear model (GLM), generalized additive model (GAM), stochastic gradient boosting machine (GBM), naïve Bayes classifier, simple artificial neural network, support vector machine (SVM), and random forest. Each model will be fully trained and hyperparameter tuned where applicable. The final model will be selected based upon AUC, sensitivity, and specificity, as well as calibration metrics on the resampled training performance. Training will occur in repeated 5-fold cross-validation with 10 repeats.

The one final model will then be assessed on the external validation data only once. 95% confidence intervals for external validation metrics will be derived using the bootstrap.

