The threshold for binary classification will either be identified on the training data alone using the AUC-based “closest-to-(0,1)-criterion” or Youden’s index to optimize both sensitivity and specificity, or will be optimized on the training set based on clinical significance (rule-out model). All analyses will be carried out in R Version 4.0.2 or more recent.²⁰

Evaluation

The performance of classification models can roughly be judged along two dimensions: Model discrimination and calibration.[46] The term *discrimination* denotes the ability of a prediction model to correctly classify whether a certain patient is going to or is not going to experience a certain outcome. Thus, discrimination described the accuracy of a binary prediction – yes or no. *Calibration*, however, describes the degree to which a model’s predicted probabilities (ranging from 0% to 100%) correspond to the actually observed incidence of the binary endpoint (true posterior). Many publications do not report calibration metrics, although these are of central importance, as a well-

calibrated predicted probability (e.g. your predicted probability of experiencing a complication is 18%) is often much more valuable to clinicians – and patients! – than a binary prediction (e.g. you are likely not going to experience a complication).²¹

Resampled training performance as well as performance on the external validation set will be assessed for discrimination and calibration.^{21,22} In terms of discrimination, we will evaluate AUC, accuracy, sensitivity, specificity, positive predictive value (PPV), negative predictive value (NPV), and F1 Score. In terms of calibration, we will assess the Brier score, expected-observed (E/O)-ratio, calibration slope and intercept, the Hosmer-Lemeshow goodness-of-fit test, as well as visual inspection of calibration plots for both datasets, which will also be included in the publication.

Interpretability

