The degree and choice of methods for interpretability will depend on the finally chosen algorithm. Some algorithms can natively provide explanations as to which factors influence the outcome in what way. Thus, in case e.g. a GLM, GAM, or naïve Bayes classifier is chosen, the parameters / partial dependence values will be provided. For simple decision trees, diagrams of the decision-making process can be provided. Other models with higher degrees of complexity, such as neural networks or stochastic gradient boosting machines cannot natively provide such explanations. In that case, we will provide both AUC-based variable importance as well as model-agnostic local interpretations of variable importance using the LIME principle.^{23,24}

Expected Results

We expect to arrive at a generalizable model based on multicenter international data that is likely to predict consistently with an AUC of at least 0.70 and that is well-calibrated. A web-based prediction tool will also be created for each of the two models using the *shiny*²⁵ environment, much akin to e.g. <https://neurosurgery.shinyapps.io/impairment> (Also see for example: Staartjes et al., Journal of Neurosurgery, 2020²⁶). This web-based app will be available for free on any internet-capable device (mobile or desktop), and should be stable on most devices due to the server-based computing. The costs for maintaining the server will be carried by the sponsor. The collected data will be stored by the sponsor for 10 years. The large dataset will be open to further analysis and will be provided to any of the contributing centers at reasonable request and after approval by all other centers. The goal is to enable other analyses using the collected dataset. If any additional analyses lead to publication, all contributors will be included as co-authors and all co-authors will have the opportunity to review said manuscript beforehand. Any contributing study center has the right to veto publication of any subsequent analyses containing their own data.

References

1. Lambeek LC, van Tulder MW, Swinkels ICS, Koppes LLJ, Anema JR, van Mechelen W. The trend in total cost of back pain in The Netherlands in the period 2002 to 2007. *Spine*. 2011;36(13):1050-1058. doi:10.1097/BRS.0b013e3181e70488

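### The expected upsampling or SMOTE step pushes predicted non-response risk upward, and nothing corrects this before the model is validated once and released as a web tool

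*SAP*

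**What the plan says.** - **Oversampling (SAP, Predictive Modeling).** "In case of major class imbalance – which is expected for the abovementioned endpoint – random upsampling or synthetic minority oversampling (SMOTE") is to be applied to the training set. What counts as major imbalance, the class ratio aimed for, and the position of this step relative to the cross-validation folds are not stated.
- **Non-response rate (SAP, Sample Size).** "Between 20% and 40% of patients report no clinically relevant improvement after spinal fusion (minority class"). The calculation uses 20%.
- **Model selection (SAP, Predictive Modeling).** Candidates are compared on AUC, sensitivity and specificity, "as well as calibration metrics on the resampled training performance". Here the resampling is repeated 5-fold cross-validation.
- **Validation (SAP, Predictive Modeling).** "The one final model will then be assessed on the external validation data only once".
- **Threshold (SAP, Predictive Modeling).** "The threshold for binary classification will either be identified on the training data alone" by a ROC-based criterion, or optimised on the training set for clinical purposes.
- **Calibration (SAP, Evaluation).** It is defined as how far "predicted probabilities (ranging from 0% to 100%) correspond to the actually observed incidence of the binary endpoint", and is measured by Brier score, E/O ratio, slope, intercept, Hosmer-Lemeshow test and plots.
- **Release (SAP, Expected Results).** The model is expected to "predict consistently with an AUC of at least 0.70 and that is well-calibrated". "A web-based prediction tool will also be created" for public use.

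The SAP contains no prior correction, intercept update or other recalibration step.

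**The concern.** A model trained on data with more non-responders than occur in practice estimates risk in that artificial population. Its ranking of patients may be unharmed, so AUC gives no warning, but its probabilities are too high for non-response and too low for success.

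The SAP treats calibration as central and holds that a calibrated probability is often worth more to clinicians and patients than a yes/no prediction. It also faults an earlier model for poor calibration. For every endpoint where oversampling is triggered, the released tool would overstate the risk of failure because of the method, not the data.

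**Working it through.** **Inputs from the SAP.** Non-response 20% to 40%, planning value 20%; 1000 training and 300 validation patients; AUC at least 0.70 expected. The planning figures reproduce: 200 / 0.20 = 1000; 300 × 0.20 = 60; 1000 + 300 = 1300.

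**Assumptions not in the SAP.** Target class ratio (50:50 unless stated), AUC exactly 0.70, logistic model with a normal linear predictor.

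**Step 1: the shift.** Raising a class from natural rate π to rate t in the training set adds logit(t) − logit(π) to the fitted logit of a likelihood-based model. At t = 0.5 the odds are multiplied by (1 − π)/π:

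- π = 0.20: 0.80/0.20 = 4, shift ln 4 = 1.386
- π = 0.30: 0.70/0.30 = 2.33, shift 0.847
- π = 0.40: 0.60/0.40 = 1.5, shift 0.405

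A true risk of 20% has odds 0.25. At π = 0.20 these become 0.25 × 4 = 1, shown as 50%. At π = 0.30 they become 0.583, shown as 37%. At π = 0.40 they become 0.375, shown as 27%.

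**Step 2: average effect at AUC 0.70, balanced to 50:50.** The Brier score of a constant prediction is π(1 − π).

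| Non-response | E/O non-response | E/O success | Brier, balanced | Brier, not resampled | Brier, constant |
|---|---|---|---|---|---|
| 20% | 2.32 | 0.67 | 0.220 | 0.146 | 0.160 |
| 30% | 1.59 | 0.75 | 0.220 | 0.188 | 0.210 |
| 40% | 1.22 | 0.85 | 0.220 | 0.212 | 0.240 |

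**Step 3: sensitivity.**

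- AUC, at 20% and 50:50: E/O is 2.40 at AUC 0.65, 2.22 at 0.75 and 2.09 at 0.80.
- Partial balancing at 20%, to 40:60: shift 0.981, E/O 1.88, a true 20% shown as 40%.
- Partial balancing at 20%, to 1:2: shift 0.693, E/O 1.59, a true 20% shown as 33%.
- Partial balancing at 30%, to 40:60: E/O 1.29.

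**Step 4: simulation at the planned size.** 200 replicates, 1000 training and 300 validation patients, logistic model with 8 predictors, AUC 0.70, 20% non-response:

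| Handling | Mean predicted risk | E/O | Calibration intercept | Brier |
|---|---|---|---|---|
| No resampling | 0.199 | 1.02 | −0.01 | 0.147 |
| Upsampling | 0.457 | 2.33 | −1.39 | 0.220 |
| SMOTE | 0.453 | 2.31 | −1.40 | 0.220 |
| Upsampling + intercept correction | 0.199 | 1.02 | −0.01 | 0.148 |

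At 40%, E/O is 1.23 for both oversampling methods.

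**Step 5: the seven algorithm types.** Assumed: 1000 training and 4000 test patients, 30 predictors of which 12 are active, untuned Python analogues, 10 replicates at 20%. Balanced to 50:50, external E/O:

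| Algorithm | Upsampling | SMOTE |
|---|---|---|
| GLM | 2.23 | 2.15 |
| GAM | 2.19 | 1.33 |
| Naive Bayes | 2.18 | 1.79 |
| Neural network | 2.03 | 1.93 |
| GBM | 2.01 | 1.37 |
| Random forest | 1.72 | 1.55 |
| SVM | 1.41 | 1.06 |

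Without resampling, E/O is 0.98 to 1.03. Brier ranges are 0.150 to 0.158 without resampling, 0.174 to 0.224 upsampled and 0.160 to 0.220 with SMOTE. With upsampling, E/O is 1.30 to 1.56 at 30% (6 replicates) and 1.13 to 1.21 at 40% (8 replicates). With SMOTE it is 1.11 to 1.55 and 1.06 to 1.20.

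**Step 6: whether the planned checks remove the shift.**

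- The threshold moves the cut-off and leaves the probability unchanged.
- Selection on calibration ranks candidates that were all trained on oversampled data. With untouched held-out folds, cross-validated E/O is still 1.33 (SVM) to 2.22 (GLM) with upsampling. If upsampling precedes the fold split, it is 1.00 to 1.06 (2 replicates only) and the error is hidden.
- External validation would reveal the error, but no action is attached to it.

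**The case against.** The strongest reply is that the headline figure rests on choices the SAP does not make. The 20% is a conservative planning value from a range reaching 40%; no target ratio is given; and the exact odds factor holds only for likelihood-based models. At 40% the effect is modest and oversampling may not be triggered. With SMOTE some algorithms shift little: the SVM has E/O 1.06, so its worse Brier score (0.184 against 0.154) is mostly not an average upward shift. The comparison with a constant prediction is also fragile. At 30% and 40:60 the Brier score is 0.196 against 0.210, and at 20% and 1:2 it is 0.162 against 0.160. All this stands as a limit on size. It does not change the direction, and the open trigger and ratio are part of the defect.

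Second, selection on calibration over untouched folds would count against the worst candidates, and the published plots would show any error. That is true, but choosing the least affected model is not correcting it. The SAP does not say that the held-out folds stay untouched, nor that they do not; the leakage point is therefore a condition to settle, not a demonstrated error.

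Third, the SAP does not forbid an intercept update before release, and does not say whether the tool shows probabilities or only a class. If it showed only a class, the training-set threshold would absorb most of the shift. However, the stated aims point to individual probabilities. An update made after the single external validation would leave the corrected model without an untouched test.

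**Conclusion.** The concern holds and should be fixed before modelling starts. Followed as written, on the path it expects, the SAP produces non-response probabilities that are too high and has no step to correct them, against its own aim of a well-calibrated tool. At its planning rate, with full balancing and a logistic model at AUC 0.70, predicted non-response is 2.3 times the observed rate. Across the stated 20% to 40% range the figure falls to 1.22, and partial balancing or other algorithms reduce it further. A Brier score worse than a constant prediction is established in the analytic logistic case at AUC 0.70 with 50:50 balancing, at 20% and 30% but not at 40%. The simulated spread across algorithms rests on untuned analogues and few replicates, so it shows direction and rough size only.

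**What to change.** Fit all candidates on the original class distribution and deal with imbalance through the training-set threshold that the SAP already provides.

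If oversampling is kept for any algorithm, the SAP should:

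1. state the trigger and the target ratio;
2. confine oversampling to the training part of each cross-validation fold;
3. compute calibration metrics on untouched held-out folds;
4. require recalibration before the model is fixed, by a prior-correction offset or by logistic recalibration on out-of-fold predictions from non-resampled training patients;
5. use the recalibrated probabilities in both the external validation and the web tool.

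The cost is SAP wording and a few lines of code, with no extra patients. In the simulation at 20%, dropping upsampling changed external AUC by at most 0.006 for six of the seven algorithms. The untuned SVM lost 0.028 (0.663 to 0.635), which is why oversampling with recalibration is left open. Dropping SMOTE changed AUC by −0.010 to +0.033. Out-of-fold logistic recalibration of the upsampled models brought external E/O to 1.00 to 1.03 for all seven.

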While even the largest cohort with millions of patients is not guaranteed to result in a robust clinical prediction model if no relevant input variables are included (“garbage in, garbage out” – do not expect to predict the future from age, gender, and body mass index), the relationship among predictive performance and sample size is certainly directly proportional, especially for some data-hungry ML algorithms. To ensure generalizability of the clinical prediction model, the sample size should be both representative enough of the patient population, and should take the complexity of the algorithm into account. For instance, a deep neural network – as an example of a highly complex model – will often require thousands of patients to converge, while a logistic regression model may achieve stable results with only a few hundreds of patients. In addition, the number of input variables plays a role. Roughly, it can be said that a bare minimum of 10 positive cases are required per included input variable to model the relationships. Often, erratic behavior of the models and high variance in performance among splits is observed when sample sizes are smaller than calculated with this rule of thumb. Of central importance is also the proportion of patients who experience the outcome. For very rare events, a much larger total sample size is consequentially needed. For instance, a prediction based on 10 input features for an outcome occurring in only 10% of cases would require at least 1000 patients including at least 100 who experienced the outcome, according to the above rule of thumb. In general and from personal experience, we do not recommend developing ML models on cohorts with less than 100 positive cases and reasonably more cases in total, regardless of the rarity of the outcome. Also, one might consider the available literature on risk factors for the outcome of interest: If epidemiological studies find only weak associations with the outcome, it is likely that one will require more patients to arrive at a model with good predictive performance, as opposed to an outcome which has several highly associated risk factors, which may be easier to predict. Larger sample sizes also allow for more generous evaluation through a larger amount of patient data dedicated to training or validation, and usually results in better calibration measures.

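### The candidate list names no penalised regression; a plain GLM fitted with all features at about 1000 patients would be expected to give risks that are too extreme, and one more candidate is a cheap improvement

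*SAP*

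**What the plan says.** The Predictive Modeling section of the SAP states "All features will initially be provided to the model for training", and also "Data will be standardized and one-hot-encoded". Recursive feature elimination is held in reserve, with no rule for when it is used. The list of seven algorithms opens with "We will trial the following algorithms for binary classification: Generalized linear model (GLM), generalized additive model (GAM" and continues with boosting, naïve Bayes, a neural network, a support vector machine and a random forest. A penalty for the GLM is neither named nor excluded; models are to be tuned where tuning applies. The final model is chosen on AUC, sensitivity, specificity and calibration metrics in repeated 5-fold cross-validation with 10 repeats. Upsampling or SMOTE is planned if class imbalance is major, which the section expects.

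The Sample Size section asks for "a minimum of 200 patients with a negative outcome (minority class) are required to extract generalizable feature relationships". It adds "For sample size calculation, we take 20% for a conservative estimate" and concludes that "1000 patients are required for training". Under Expected Results the aim is a model with an "AUC of at least 0.70 and that is well-calibrated".

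**The concern.** A logistic GLM fitted by maximum likelihood to many columns and few failures overfits. Its coefficients are too large on average, so high predicted risks come out too high and low ones too low. This shows as a calibration slope below 1 in new patients, even when the mean risk is right. Feature elimination chooses columns but does not shrink the coefficients that stay. Height, weight and BMI all enter and are nearly collinear, which adds to the instability.

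The Evaluation section puts a well-calibrated individual probability above a yes/no prediction, and the introduction faults an earlier model for poor calibration on external validation. The product is a public web tool that shows individual risks. Penalised regression is the standard means of limiting this overfitting while keeping a simple, readable model, and it is the one regression option that the list does not name.

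**Working it through.** **1. The plan's own figure.** 200 failures / 0.20 = 1000 training patients. This reproduces.

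**2. Number of parameters.** The Features section lists 19 items. Assumed coding: 7 indications, 6 index segments (T12 to S1), 2 for smoking, 3 for race, 4 for approach and 14 single items, so 7 + 6 + 2 + 3 + 4 + 14 = 36. Coarser coding gives about 31. Failures per listed item: 200/19 = 10.5. Failures per coded column: 200/36 = 5.6.

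**3. Expected slope in closed form.** The expected uniform shrinkage S of an unpenalised fit solves

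n = P / [(S − 1) ln(1 − R²/S)],

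where P is the number of parameters and R² is the Cox-Snell value. A normal linear predictor with SD 0.777 and 20% failures gives an AUC of 0.70 and R² = 0.0806. For P = 36, S = 0.704 solves it: ln(1 − 0.0806/0.704) = −0.1216, and 36 / (0.296 × 0.1216) ≈ 1000. For S = 0.90: ln(1 − 0.0806/0.90) = −0.0938, and 36 / (0.10 × 0.0938) ≈ 3840 patients.

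| Failures | True AUC | P | Expected slope, n = 1000 |
|---|---|---|---|
| 20% | 0.65 | 36 | 0.57 |
| 20% | 0.70 | 36 | 0.70 |
| 20% | 0.70 | 31 | 0.73 |
| 20% | 0.70 | 19 | 0.82 |
| 20% | 0.75 | 36 | 0.79 |
| 20% | 0.80 | 36 | 0.85 |
| 40% | 0.70 | 36 | 0.78 |

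**4. Simulation without rebalancing.** n = 1000, slope measured in 20,000 new patients, 80 to 100 runs per setting. The ridge penalty was tuned by log-loss in 5-fold cross-validation with 2 repeats (the plan has 10).

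| Setting | Plain GLM, mean slope | Ridge, mean slope |
|---|---|---|
| 20%, AUC 0.70, P = 36 | 0.66 | 1.05 |
| 20%, AUC 0.75, P = 36 | 0.72 | 1.01 |
| 40%, AUC 0.70, P = 36 | 0.72 | 1.00 |
| 20%, AUC 0.70, P = 19 | 0.80 | 1.04 |

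In the first setting the 5–95% range was 0.55–0.76 for the plain GLM and 0.78–1.39 for ridge. Of the ridge fits, 39% lay within 0.9–1.1, 21% below and 40% above. The AUC in new patients was 0.668 against 0.669. Separate simulations with 31 and 33 columns agreed on the means. At 20% failure their single ridge fits reached about 1.6. With 31 columns the plain slope rose to 0.83 at n = 2000 and 0.87 at n = 3000.

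**5. The tuning criterion matters.** With the penalty tuned on AUC instead of log-loss (first setting), the median slope was 0.99 but the 5–95% range was 0.62–5.13.

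**6. With the planned rebalancing.** 33 columns, 20% failures, random upsampling:

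| Fit | Mean slope |
|---|---|
| Plain GLM | 0.61 |
| Ridge, upsampled before the folds | 0.70 |
| Ridge, upsampled inside the folds | 0.85 |

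The E/O ratio stayed near 2.3 with ridge. This is plausible: a balanced training set has 50% failures, and 0.50/0.20 = 2.5 would be the ratio for an uninformative model. With 31 columns the upsampled Brier score was 0.227 for the plain GLM and 0.225–0.226 for ridge.

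**The case against.** The strongest reply is that nothing in the section is wrong. A list of seven algorithms without an eighth is a design choice. The GLM is only one candidate, calibration counts in the selection, and the slope is reported at external validation, so a poor GLM can be rejected or at least seen. The 1000 is a minimum, and the plan says that more data should improve calibration. All of this stands. It makes the harm conditional, but rejecting the GLM cannot supply a candidate that is not on the list.

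Four stronger readings are tempting and are not supported:

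- That the plan prescribes an unpenalised GLM. It is silent. An ordinary GLM has no tuning parameter, so the general remark on tuning supplies no shrinkage, but a penalised fit is not ruled out.
- That a penalty removes the overfitting. It corrects the slope on average. Each outcome gets one model, and a single ridge fit can still miss in either direction.
- That this change alone makes the tool well calibrated. Under the planned rebalancing the inflated mean risk dominates, and the penalty barely moves the Brier score.
- That the plan breaks its own rule of "a bare minimum of 10 positive cases are required per included input variable to model the relationships". Counted by listed item the rule is met (10.5); it fails only if coded columns are counted (5.6).

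Nor is it shown that the finally selected model would be better. One selection simulation moved the chosen model's slope from 0.81 to 1.05 and its Brier score from 0.151 to 0.149. It used five of the seven algorithms, a linear truth, a fixed penalty and a ranking rule that is not in the plan.

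**Conclusion.** The point holds as a cheap improvement and not as an error in the plan. If the GLM is fitted without a penalty to all features at the planned minimum, and is selected, its risks are expected to be too extreme: slope about 0.65–0.75 at a true AUC near 0.70, and about 0.82 with 2000 patients. A log-loss-tuned penalised GLM on unrebalanced data brings the mean slope close to 1 with no loss of AUC. It improves the mean slope under upsampling as well, but does not repair the inflated mean risk there.

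The sizes rest on assumptions that the SAP does not give: 31 to 36 coded columns, the spread of true effects, ridge as the penalty, and random upsampling in place of SMOTE. The direction was the same at every AUC from 0.65 to 0.80. The effect is small only with a high AUC and few parameters.

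**What to change.** In the SAP, Predictive Modeling, add to the list of algorithms: a penalised GLM (ridge or elastic net), with the penalty tuned by log-loss in the same repeated 5-fold cross-validation. State that this candidate is fitted without upsampling or SMOTE, or that its risks are recalibrated to the original incidence before they are assessed or shown. The plain GLM may stay on the list. If a penalised GLM was intended all along, the same sentence makes that clear.

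The cost is a line or two of SAP text and one more fit per outcome. The coefficients are shrunk, so they are reported without classical p-values. No further data or patients are needed.

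### The repeated cross-validation result that tunes and selects the model is also the internal performance result: negligible optimism for AUC, about 0.02 to 0.03 for sensitivity + specificity if the cut-off is chosen on the same predictions

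*SAP*

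**What the plan says.** The Predictive Modeling section lists seven candidate algorithms (GLM, GAM, gradient boosting, naïve Bayes, a simple neural network, SVM, random forest). On tuning: "Each model will be fully trained and hyperparameter tuned where applicable". It names one resampling scheme: "Training will occur in repeated 5-fold cross-validation with 10 repeats". The choice among candidates rests on that scheme: "The final model will be selected based upon AUC, sensitivity, and specificity, as well as calibration metrics on the resampled training performance". If feature selection is needed, "we will apply recursive feature elimination (RFE) to select input features on the training data"; whether this is repeated within folds is not stated. On the cut-off: "The threshold for binary classification will either be identified on the training data alone", by Youden's index or the closest-to-(0,1) criterion, or else optimised on the training set for clinical significance as a rule-out model.

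The Evaluation section then makes the same quantity a result: "Resampled training performance as well as performance on the external validation set will be assessed for discrimination and calibration". The metrics listed are AUC, accuracy, sensitivity, specificity, PPV, NPV, F1 and several calibration measures. The plan also has a real safeguard: the one selected model is applied to the external data a single time, and bootstrap confidence intervals are specified for the external metrics.

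**The concern.** A score that has been maximised over many candidates is, on average, too high for the candidate that wins. Here the resampled training performance picks the algorithm and, as far as the text shows, the hyperparameters, and is then assessed as internal performance. Ten repeats reduce the noise from random splitting. They do not remove this bias, because every repeat uses the same patients.

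The cut-off adds a second, separate source. If it is chosen to optimise sensitivity and specificity on the same resampled predictions on which they are reported, both are optimised for those patients. Accuracy, PPV, NPV and F1 depend on the same cut-off.

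What is at stake is the comparison between internal and external results. A lower external figure invites the reading that the model travels poorly to new centers, when part of the drop may be optimism in the internal figure.

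**Working it through.** **1. The plan's own figures.** The Sample Size section assumes 20% in the minority class. 200 / 0.20 = 1000 for training; 300 × 0.20 = 60 minority-class patients at external validation; 1000 + 300 = 1300. All three reproduce. The Expected Results section expects an AUC of at least 0.70. The plan gives no figure for optimism, so the rest uses these sizes plus stated assumptions.

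**2. Sampling error of the AUC (Hanley-McNeil).** With A = 0.70, Q1 = A/(2−A) = 0.538 and Q2 = 2A²/(1+A) = 0.576,

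SE = √{[A(1−A) + (n₁−1)(Q1−A²) + (n₀−1)(Q2−A²)] / (n₁n₀)}.

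- Training, 200/800: SE = 0.022.
- External, 60/240: SE = 0.041.

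**3. AUC optimism from picking the best of seven, analytic.** If all seven have the same true AUC and their cross-validated AUCs have pairwise correlation ρ (assumed; not in the plan), the expected excess is E[max of 7 standard normals] × SE × √(1−ρ) = 1.352 × 0.0222 × √(1−ρ).

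| ρ | Excess, equal true AUCs | Excess, true AUCs differing with SD 0.01 |
|---|---|---|
| 0.5 | 0.021 | 0.018 |
| 0.8 | 0.013 | 0.010 |
| 0.9 | 0.0095 | 0.005 |
| 0.95 | 0.007 | 0.003 |

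The plan does not state the size of the tuning grid. With 50 effective candidates at ρ = 0.8 the equal-AUC figure is 2.249 × 0.0222 × √0.2 = 0.022.

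**4. AUC optimism, simulated.**

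- *Seven algorithm families, 16 tuned configurations* (200 data sets, 1000 patients, about 19% events, 25 features, 5-fold with 2 repeats, selection on AUC). The winner's cross-validated AUC was 0.676. The true AUC of models trained on 80% of the patients was 0.672, an excess of 0.004 (SE 0.002). The true AUC of the model refitted on all training patients was 0.675, an excess of 0.001 (SE 0.002). The selection component alone was 0.007 (SE 0.001). It is largely offset because cross-validation scores models built on fewer patients than the final one.
- *Six simple learner families, 46 settings* (1000 patients, about 20% events, 31 coded inputs, 3 to 10 repeats). Excess over the same fold models: 0.004 (SE 0.003) at AUC 0.73, 0.008 (SE 0.003) at AUC 0.65, and 0.031 (SE 0.003) with no signal at all.

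**5. Cut-off optimism.** Binormal scores with AUC 0.70 have separation √2 × Φ⁻¹(0.70) = 0.742. The best attainable sensitivity + specificity − 1 is 2Φ(0.371) − 1 = 0.289. Choosing the cut-off on the scores it is reported for overstates the true value at that cut-off as follows:

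| Minority / majority | Youden | Closest-to-(0,1) |
|---|---|---|
| 200 / 800 | 0.031 to 0.033 | 0.022 to 0.023 |
| 400 / 600 | 0.024 to 0.025 | 0.016 |

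The ranges span separate simulation runs. Relative to 0.289, 0.031 is 11% and 0.024 is 8%.

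**6. Scale.** With sensitivity = specificity = 0.645, the SE of their sum is √(0.645 × 0.355 × (1/n₁ + 1/n₀)): 0.069 externally (60/240) and 0.038 internally (200/800).

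**The case against.** Several counter-arguments are strong, and most of them stand.

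- **The main evidence is clean.** The selected model meets the external data once, with the cut-off already fixed. None of the bias described here reaches those figures. This stands in full.
- **The AUC effect is close to nothing.** With signal it is 0.004 to 0.008 against the fold models and 0.001 (SE 0.002) against the refitted model. The 0.031 needs a model with no signal, which is not what the plan expects. A reader might infer that the internal AUC will be materially inflated; these figures do not support that. The offset from training on 80% of patients was shown for AUC only, not for sensitivity and specificity.
- **The larger number comes from the cut-off, not from choosing among algorithms.** True: it would arise with one untuned model. It also depends on the route taken. The plan allows a rule-out threshold, for which no figure was derived, and does not say whether the cut-off is set within folds or on pooled predictions.
- **The excess is small beside the external uncertainty.** At 0.031 to 0.033 it is under half of the external SE of 0.069. But it is systematic, always flatters the internal side, and can be avoided.
- **A single loop is inferred.** A reader might take the plan to rule out nesting. It neither states nor excludes it; it names one scheme and uses its output for both purposes. Likewise, publication of internal AUC, sensitivity and specificity is a reasonable reading, not stated text. What is expressly promised is "visual inspection of calibration plots for both datasets, which will also be included in the publication".
- **The simulations are not the plan.** They use assumed signal, assumed grids and AUC-only selection. That limits the precision of the size, not the direction.

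**Conclusion.** The point holds as a limited reporting problem that should be corrected. The same resampled performance serves as selection criterion and as internal result, the cut-off is set on the same patients, and nothing in the SAP adjusts for either. The internal figures are therefore optimistic in expectation.

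The AUC part is negligible if the model has signal. The part worth acting on is sensitivity + specificity, about 0.02 to 0.03 too high, with the metrics that share the cut-off also affected. This assumes AUC 0.70, 200/800 patients, and a Youden or closest-to-(0,1) cut-off chosen on the predictions it is reported for. A larger tuning grid, or feature elimination done once outside the folds, could add to the optimism.

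Two stronger conclusions are not supported: that the plan's performance evidence as a whole is compromised, and that any fall from internal to external performance would be mainly selection optimism. The external validation is unbiased in this respect and should carry the claims.

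**What to change.** State in Predictive Modeling that the repeated 5-fold cross-validation is a selection criterion only. Report internal performance from an outer 5-fold loop. On each outer training part, repeat every data-dependent step: KNN imputation, upsampling or SMOTE, RFE, tuning, algorithm choice and cut-off choice. Score the result on the untouched outer fold, and use this figure as the comparator for the external result.

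This requires one pre-stated ranking rule for the algorithm choice, for example AUC first, because the plan's several criteria carry no weights and cannot otherwise be repeated automatically in each fold.

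As a minimum without the outer loop: choose the cut-off on the training folds and score it on the held-out fold, label the internal figures as selection-stage results, and base performance claims on the external validation.

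The cost is SAP wording, including the ranking rule, about five times the computing time for the full version, and slightly less favourable internal figures. No new data are needed.
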